Safety and tolerability will be assessed based on the following:

- Incidence, type, seriousness, and severity of AEs reported;
- Clinical laboratory investigations (hematology, serum chemistry, urinalysis);
- Vital signs (blood pressure, heart rate, and body temperature);
- 12-lead ECGs;
- Physical examinations; and
- ECOG performance status.

Statistical Methods

Sample Size Justification and Interim Analysis

The enrollment planned for this study is approximately 360 patients, with up to approximately 150 patients in Cohort A with measurable visceral and/or nodal disease (ie, up to 100 patients with a deleterious BRCA1/2 mutation [with a maximum of 60 patients who have only measurable lymph node disease], and up to approximately 50 patients with a deleterious ATM mutation), up to approximately 150 patients in Cohort B (ie, up to approximately 100 patients with a deleterious BRCA1/2 mutation and 50 patients with a deleterious ATM mutation), and up to approximately 60 patients in Cohort C.

Cohort A

Cohort A will be divided into 2 sub-cohorts defined by deleterious gene mutation (BRCA1/2 vs. ATM).

Cohort A (BRCA1/2)

A Simon 2-stage design to evaluate confirmed ORR by modified RECIST Version 1.1 criteria per investigator will be used. With rolling enrollment, after the first 37 patients with a deleterious BRCA1/2 mutation have either: a) completed 16 weeks of treatment or b) discontinued treatment prior to completing, an interim analysis will be performed (ie, Stage 1). If $\leq 8/37$ patients in Stage 1 have a confirmed objective response (CR or PR per

investigator and without progression in bone per PCWG3), the DMC will evaluate the overall benefit/risk for patients with deleterious BRCA1/2 mutations in this cohort and make a recommendation whether further enrollment should be discontinued. If $\geq 9/37$ patients have a confirmed objective response, then enrollment will continue with additional patients in Stage 2. With 83 total patients with a deleterious BRCA1/2 mutation, characteristics of the Simon 2-stage design include:

- 5% probability of accepting a minimally effective drug
- 90% probability of accepting an effective drug
- ORR of 20% for a minimally effective drug
- ORR of 35% for an effective drug

If there are at least 23 responses in 83 patients with a deleterious BRCA1/2 mutation, the null hypothesis (ORR = 20%) will be rejected. This design yields a type I error rate of 5% and power of 90% when the true response rate is 35%.

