Cohort B will be divided into 2 sub-cohorts defined by deleterious gene mutation (BRCA1/2 vs. ATM). Cohort B will be enrolled concurrently with Cohort A and is expected to enroll at approximately the same rate as Cohort A. Enrollment in Cohort B will be halted when Cohort A (BRCA1/2) is fully enrolled. Therefore, it is anticipated that up to approximately 150 patients may be enrolled in Cohort B.

Cohort B (BRCA1/2)

A Simon 2-stage type futility rule will be employed in Cohort B (BRCA1/2). An interim analysis (Stage 1) will be performed after the first 19 patients have either: a) completed 16 weeks of treatment; or b) discontinued treatment prior to completing. Enrollment into the study will continue while this interim analysis occurs. If $\leq 4/19$ patients in Stage 1 have a PSA response ($\geq 50\%$ decrease), the DMC will evaluate the overall benefit/risk for patients with deleterious BRCA1/2 mutations in this cohort and make a recommendation whether further enrollment should be discontinued. If $\geq 5/19$ patients have a PSA response, then enrollment will continue in Stage 2. With 54 total patients with a deleterious BRCA1/2 mutation, characteristics of the Simon 2-stage design include:

- 5% probability of accepting a minimally effective drug
- 90% probability of accepting an effective drug
- ORR of 20% for a minimally effective drug
- ORR of 40% for an effective drug

If there are at least 16 responses in 54 patients with a deleterious BRCA1/2 mutation, the null hypothesis (ORR = 20%) will be rejected. This design yields a type I error rate of 5% and power of 90% when the true response rate is 40%. Additionally, if the criteria for Stage 2 are met, additional patients, up to approximately 100 total, may be enrolled. Enrollment in Cohort B (BRCA1/2) will be halted when Cohort A (BRCA1/2) is fully enrolled.

Cohort B (ATM)

Patients in Cohort B (ATM), having a deleterious ATM mutation, will be enrolled concurrently with patients from Cohort B (BRCA1/2). It is expected that about 1/3 of the Cohort B patients will have deleterious ATM mutations. If 100 patients are enrolled in Cohort B (BRCA1/2), then approximately 50 patients would be expected to enroll into Cohort B (ATM).

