11.2 Determination of Sample Size

The enrollment planned for this study is approximately 360 patients, with up to approximately 150 patients in Cohort A with measurable visceral and/or nodal disease (ie, up to 100 patients with a deleterious BRCA1/2 mutation [with a maximum of 60 patients who have only measurable lymph node disease], and up to approximately 50 patients with a deleterious ATM mutation), up to approximately 150 patients in Cohort B (ie, up to approximately 100 patients with a deleterious BRCA1/2 mutation and 50 patients with a deleterious ATM mutation), and up to approximately 60 patients in Cohort C.

Cohort A

Cohort A will be divided into 2 sub-cohorts defined by deleterious gene mutation (BRCA1/2 vs. ATM).

Cohort A (BRCA1/2)

A Simon 2-stage design to evaluate confirmed ORR by modified RECIST Version 1.1 criteria per investigator will be used. Characteristics of the Simon 2-stage design include:

- 5% probability of accepting a minimally effective drug
- 90% probability of accepting an effective drug
- ORR of 20% for a minimally effective drug
- ORR of 35% for an effective drug

In the first stage, 37 patients with a deleterious BRCA1/2 mutation will be evaluated. If the study is to proceed to the second stage, additional patients with a deleterious BRCA1/2 mutation will be accrued for a total of 83.

Note: If the study is to proceed to Stage 2, additional patients with a deleterious BRCA1/2 mutation up to 100 total patients (and a maximum of 60 patients with only measurable lymph node disease) will be enrolled in Cohort A (BRCA1/2) if additional clinical data is requested by the regulatory authorities to support regulatory filing. If sufficient evidence exists to support a regulatory filing prior to fully enrolling Cohort A (BRCA1/2), enrollment may be discontinued early.

Cohort A (ATM)

Patients in Cohort A (ATM), having a deleterious ATM mutation, will be enrolled concurrently with patients from Cohort A (BRCA1/2). It is expected that about 1/3 of the Cohort A patients will have deleterious ATM mutations. If 100 patients are enrolled in Cohort A (BRCA1/2), then approximately 50 patients would be expected to enroll into Cohort A (ATM).

A Simon 2-stage design to evaluate confirmed ORR by modified RECIST Version 1.1 criteria per investigator will be used. Characteristics of the Simon 2-stage (minimax) design include:

- 5% probability of accepting a minimally effective drug
- 80% probability of accepting an effective drug

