11.7 Interim Analysis

Cohort A

As described in [Section 11.2](#), up to approximately 150 patients will be enrolled in Cohort A, which will be divided into 2 sub-cohorts defined by deleterious gene mutation (BRCA1/2 vs. ATM).

Cohort A (BRCA1/2)

A Simon 2-stage design to evaluate confirmed ORR by modified RECIST Version 1.1 criteria per investigator will be used. With rolling enrollment, after the first 37 patients with a deleterious BRCA1/2 mutation have either: a) completed 16 weeks of treatment, or b) discontinued treatment prior to completing, an interim analysis will be performed (ie, Stage 1). If $\leq 8/37$ patients in Stage 1 have a confirmed objective response (CR or PR per investigator and without progression in bone per PCWG3), the DMC will evaluate the overall benefit/risk for patients with deleterious BRCA1/2 mutations in this cohort and make a recommendation whether further enrollment should be discontinued. If $\geq 9/37$ patients have a confirmed objective response, then enrollment will continue with additional patients in Stage 2. With 83 total patients with a deleterious BRCA1/2 mutation, characteristics of the Simon 2-stage design include:

- 5% probability of accepting a minimally effective drug
- 90% probability of accepting an effective drug

- ORR of 20% for a minimally effective drug
- ORR of 35% for an effective drug

Cohort A (ATM)

A Simon 2-stage type futility rule will be employed in Cohort A (ATM). An interim analysis (Stage 1) will be performed after the first 31 patients have either: a) completed 16 weeks of treatment; or b) discontinued treatment prior to completing. Enrollment into the study will continue while this interim analysis occurs. If $\leq 6/31$ patients in Stage 1 have a confirmed objective response (CR or PR per investigator and without progression in bone per PCWG3), the DMC will evaluate the overall benefit/risk for patients with deleterious ATM mutations in this cohort and make a recommendation whether further enrollment should be discontinued. If $\geq 7/31$ patients have a confirmed objective response, then enrollment will continue in Stage 2. With 53 total patients with a deleterious ATM mutation, characteristics of the Simon 2-stage (minimax) design include:

- 5% probability of accepting a minimally effective drug
- 80% probability of accepting an effective drug
- ORR of 20% for a minimally effective drug
- ORR of 35% for an effective drug

Cohort B

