13.6 Data Monitoring Committee

A DMC will be established to review safety data in compliance with a prospective charter. For Cohort A and B, DMC may be requested to evaluate the overall risk/benefit of rucaparib therapy in this patient population based on the outcome of Stage 1 interim analysis. The DMC will be comprised of study investigators and of sponsor representatives. The DMC responsibilities, authorities, and procedures for this study will be documented in the DMC charter, which will be endorsed by the DMC members and signed by the DMC chair prior to the first data review meeting. The DMC will also ensure the study is beneficial to patients (see [Section 11.7](#)).

The DMC will meet after the first 20 patients received rucaparib for at least 28 days or discontinued study treatment, and then at least semi-annually after sufficient data has been collected. The DMC chairperson or sponsor may convene an unscheduled DMC meeting if there are newly identified significant safety concerns. Following data review, the DMC will recommend continuation, revision, or termination of the study and/ or continuing or halting enrollment into a particular subgroup. Details regarding the DMC will be in the committee charter.

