2.3 Sample Size Justification

The enrollment planned for this study is approximately 360 patients, with up to approximately 150 patients with measurable visceral and/or nodal disease in Cohort A (ie, up to 100 patients with a deleterious BRCA1/2 mutation [with a maximum of 60 patients who have only measurable lymph node disease], and up to approximately 50 patients with a deleterious ATM mutation); up to approximately 150 patients without measurable disease in Cohort B (ie, up to approximately 100 patients with a deleterious BRCA1/2 mutation and 50 patients with a deleterious ATM mutation); and up to approximately 60 patients with or without measurable visceral and/or nodal disease who have a deleterious mutation in a HRR gene other than BRCA1/2 or ATM in Cohort C.

Cohort A

Cohort A will be divided into 2 sub-cohorts defined by deleterious gene mutation (BRCA1/2 vs. ATM).

Cohort A (BRCA1/2)

A Simon 2-stage design to evaluate confirmed ORR by modified RECIST Version 1.1 criteria per investigator will be used. With rolling enrollment, after the first 37 patients with a

deleterious BRCA1/2 mutation have either: a) completed 16 weeks of treatment or b) discontinued treatment prior to completing, an analysis will be performed (ie, Stage 1). If $\leq 8/37$ patients in Stage 1 have a confirmed objective response (CR or PR per investigator and without progression in bone per PCWG3), the data monitoring committee (DMC) will evaluate the overall benefit/risk for patients with deleterious BRCA1/2 mutations in this cohort and make a recommendation whether further enrollment should be discontinued. If $\geq 9/37$ patients have a confirmed objective response, then enrollment will continue with additional patients in Stage 2. With 83 total patients with a deleterious BRCA1/2 mutation, characteristics of the Simon 2-stage design include:

- 5% probability of accepting a minimally effective drug
- 90% probability of accepting an effective drug
- ORR of 20% for a minimally effective drug
- ORR of 35% for an effective drug

If there are at least 23 responses in 83 patients with a deleterious BRCA1/2 mutation, the null hypothesis (ORR = 20%) will be rejected. This design yields a type I error rate of 5% and power of 90% when the true response rate is 35%.

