A Simon 2-stage type futility rule will be employed in Cohort B (BRCA1/2). The Stage 1 analysis will be performed after the first 19 patients have either: a) completed 16 weeks of treatment; or b) discontinued treatment prior to completing. Enrollment into the study will continue while this analysis occurs. If $\leq 4/19$ patients in Stage 1 have a PSA response ($\geq 50\%$ decrease from baseline), the DMC will evaluate the overall benefit/risk for patients with a deleterious BRCA1/2 mutation in this sub-cohort and make a recommendation whether further enrollment should be discontinued. If $\geq 5/19$ patients have a PSA response, then enrollment will continue in Stage 2. With 54 total patients with a deleterious BRCA1/2 mutation, characteristics of the Simon 2-stage design include:

- 5% probability of accepting a minimally effective drug
- 90% probability of accepting an effective drug
- ORR of 20% for a minimally effective drug
- ORR of 40% for an effective drug

If there are at least 16 responses in 54 patients with a deleterious BRCA1/2 mutation, the null hypothesis (ORR = 20%) will be rejected. This design yields a type I error rate of 5% and power of 90% when the true response rate is 40%. Additionally, if the criteria for Stage 2 are met, additional patients, up to approximately 100 total, may be enrolled. Enrollment in Cohort B (BRCA1/2) will be halted when Cohort A (BRCA1/2) is fully enrolled.

Cohort B (ATM)

Patients in Cohort B (ATM), having a deleterious ATM mutation, will be enrolled concurrently with patients from Cohort B (BRCA1/2). It is expected that about 1/3 of the Cohort B patients will have a deleterious ATM mutation. If 100 patients are enrolled in Cohort B (BRCA1/2), then approximately 50 patients would be expected to enroll in Cohort B (ATM).

A Simon 2-stage type futility rule will be employed. The Stage 1 analysis will be performed after the first 18 patients have either: a) completed 16 weeks of treatment; or b) discontinued treatment prior to completing. Enrollment into the study will continue while this analysis occurs. If $\leq 4/18$ patients in Stage 1 have a PSA response ($\geq 50\%$ decrease from baseline), the DMC will evaluate the overall benefit/risk for patients with a deleterious ATM mutation in this cohort and make a recommendation whether further enrollment should be

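### The 5% type I error stated without condition for the two BRCA1/2 Simon rules assumes that the advisory Stage 1 stop is followed; for the test at 83 or 54 patients it could reach 5.7% (Cohort A) or 6.0% (Cohort B).

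*Protocol*

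**What the plan says.** **Cohort A (BRCA1/2).** The synopsis and SAP 2.3 set Stage 1 at 37 patients, with continuation at 9 or more responses. The final rule in SAP 2.3 is "If there are at least 23 responses in 83 patients with a deleterious BRCA1/2 mutation, the null hypothesis (ORR = 20%) will be rejected". The synopsis then states "This design yields a type I error rate of 5% and power of 90% when the true response rate is 35" (percent).

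**Cohort B (BRCA1/2).** Stage 1 has 19 patients, with continuation at 5 or more PSA responses. The null is rejected at 16 or more responses in 54. The synopsis states "This design yields a type I error rate of 5% and power of 90% when the true response rate is 40" (percent).

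**What happens when Stage 1 is missed.** At 8/37 or fewer, the synopsis has the DMC evaluate "benefit/risk for patients with deleterious BRCA1/2 mutations in this cohort and make a recommendation whether further enrollment should be discontinued". SAP 2.3 uses the same form for Cohort B: "mutation in this sub-cohort and make a recommendation whether further enrollment should be discontinued". SAP 11.4 describes the futility analyses as helping to assess whether each sub-cohort should go on, and for Cohort B (BRCA1/2) mentions only a DMC evaluation. Protocol 13.6 lets the DMC recommend "continuing or halting enrollment into a particular subgroup".

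**Link between the stages.** Protocol 11.2 says "If the study is to proceed to the second stage, additional patients with a deleterious BRCA1/2 mutation will be accrued", so Stage 2 is tied to proceeding. Neither document says that a sub-cohort allowed to proceed after missing the boundary loses the final test.

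**Enrollment.** Both sub-cohorts may grow to about 100 patients. No rejection count is given for that size.

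**The concern.** The type I error of a Simon two-stage design depends on the stop. A trial that misses Stage 1 counts as a non-rejection, whatever its later responses would have been. If such a trial may continue and then be tested against the same final cut-off, some extra null trials reject, and the error rate rises above the design value.

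Here the stop is a recommendation, while the 5% is stated with no condition. If the DMC let a sub-cohort continue after a missed boundary and it later reached 23/83 or 16/54, calling that a rejection at 5% would be slightly too favourable. The situation is not remote under the null: at a true rate of 20%, Stage 1 is missed in 68.6% of Cohort A trials and 67.3% of Cohort B trials.

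**Working it through.** **Inputs** (synopsis; SAP 2.3). Null rate 20% in both cohorts.
- Cohort A (BRCA1/2): n1 = 37, Stage 1 missed at 8 or fewer, n = 83, reject at 23 or more, alternative 35%.
- Cohort B (BRCA1/2): n1 = 19, Stage 1 missed at 4 or fewer, n = 54, reject at 16 or more, alternative 40%.

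**Step 1: reproduce the plan's figures, stop followed.** With r1 the Stage 1 boundary and r the final cut-off,

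P(reject) = Σ over x1 > r1 of P(X1 = x1) × P(X2 ≥ r − x1), where X1 ~ Bin(n1, p) and X2 ~ Bin(n − n1, p).

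- Cohort A: type I error 0.0487, power 0.9009.
- Cohort B: type I error 0.0482, power 0.9045.

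Both agree with the stated 5% and 90%.

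**Step 2: override only results exactly on the boundary.** Add the term for x1 = r1.
- Cohort A: P(X1 = 8) × P(X2 ≥ 15 of 46) = 0.1529 × 0.0304 = 0.0047. Type I error is 0.0487 + 0.0047 = 0.0534.
- Cohort B: P(X1 = 4) × P(X2 ≥ 12 of 35) = 0.2182 × 0.0344 = 0.0075. Type I error is 0.0482 + 0.0075 = 0.0557.

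**Step 3: override every crossing.** Stage 1 then plays no part, and P(reject) = P(X ≥ r), X ~ Bin(n, p).
- Cohort A: P(X ≥ 23 of 83) = 0.0568, an increase of 0.0081.
- Cohort B: P(X ≥ 16 of 54) = 0.0597, an increase of 0.0115.

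| Stage 1 stop | A: type I error | A: power | B: type I error | B: power |
|---|---|---|---|---|
| Followed | 4.9% | 90.1% | 4.8% | 90.4% |
| Overridden at 8/37 or 4/19 only | 5.3% | 92.3% | 5.6% | 94.2% |
| Overridden at every crossing | 5.7% | 93.6% | 6.0% | 95.7% |

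**Step 4: how much overriding 5% can absorb.** Discreteness leaves 0.0500 − 0.0487 = 0.0013 in Cohort A and 0.0500 − 0.0482 = 0.0018 in Cohort B. Assume that the chance of an override does not depend on the Stage 1 count. Then the share of crossings that can be overridden at 5% or less is 0.0013/0.0081, about 16%, in Cohort A, and 0.0018/0.0115, also about 16%, in Cohort B.

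**Step 5: the ATM rules.** The Step 3 calculation gives 0.0512 for 16/53 and 0.0508 for 11/33. Both still round to 5%.

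**Step 6: scope of the Step 3 values.** They are maxima for one test at exactly 83 or 54 patients. As an illustration only, assume a second look at 100 patients with a cut-off of 28, which the documents do not contain. Ignoring Stage 1, the chance under the null of rejecting at either look is 6.3% for 23/83 then 28/100, and 7.5% for 16/54 then 28/100.

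**The case against.** The best defence is that the sentence describes a named design. It follows a list of Simon design characteristics, and stopping at Stage 1 is part of that design. Protocol 11.2 and SAP 11.4 tie Stage 2 to proceeding, and quoting nominal properties is ordinary practice. This stands to the extent that the arithmetic is correct. It does not supply the missing condition, because the plan departs from the named design at the point on which its error rate depends, and the sentence does not say so.

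A second defence is that little depends on the figure. The primary analyses (Protocol 11.5.1, SAP 10.1) are response rates with 95% confidence intervals, and the Cohort A rule uses investigator response while the primary endpoint is by independent review. This stands, and it is why the point is minor. The interval method is not stated. If exact limits are assumed, 23/83 gives 18.4% to 38.6% and 16/54 gives 18.0% to 43.6%. Both include 20%, so a marginal rejection would look marginal.

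A reader might infer more than the documents support:
- *That the cut-offs or the 5% and 90% are miscalculated.* They reproduce.
- *That any departure from the stop breaks 5%.* Step 4 shows room for rare overrides.
- *That 5.7% and 6.0% cap the error of the whole plan.* Enrollment may reach 100 with no rejection count, so no plan-wide cap can be derived.
- *That the ATM rules need the same correction.* At 5.1% they still agree with the stated 5%.

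**Conclusion.** The point holds as a missing condition. The stated 5% is the value when the Stage 1 stop is followed, and the advisory stop does not guarantee it. The largest excess over the stop-followed value is 0.8 percentage points in Cohort A (BRCA1/2) and 1.2 in Cohort B (BRCA1/2), with a gain in power in each case. This rests on three assumptions: a true rate of exactly 20%, a single test at exactly 83 or 54 patients, and every crossing overridden. How often the DMC would override cannot be known from the documents, so 5.7% and 6.0% are extremes for that test and not expected values. Severity is minor.

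**What to change.** Keep the cut-offs. In the synopsis and SAP 2.3, replace the type I error and power sentence for the two BRCA1/2 sub-cohorts with:

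> Type I error is 5% and power 90% if the Stage 1 stop is followed and the test is made at 83 (Cohort A BRCA1/2) or 54 (Cohort B BRCA1/2) patients; because the stop is non-binding, type I error for that test could be as high as 5.7% and 6.0% respectively, with power up to 93.6% and 95.7%.

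The alternative rates of 35% and 40% should stay attached to the power figures. Do not describe the new values as ceilings for the plan, and leave the ATM text unchanged.

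The cost is wording only. Sample size, cut-offs and the DMC's role do not change. The one drawback is a slightly less favourable stated type I error.

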2 LIST OF ABBREVIATIONS AND DEFINITIONS OF TERMS

99m Tc MDP	99m technecium methyl diphosphonate
ADP	adenosine diphosphate
ADT	androgen deprivation therapy
AE	adverse event
AESI	adverse event of special interest
AIDS	acquired immunodeficiency syndrome
ALCOA+	Attributable, Legible, Contemporaneous, Original or Certified Copy, Accurate, and 'Plus' (+) Complete, Consistent, Enduring, and Available
ALT	alanine aminotransferase
AML	acute myeloid leukemia
ANC	absolute neutrophil count
AR	androgen receptor
AST	aspartate aminotransferase
ATM	ataxia telangiectasia mutated serine/threonine kinase
ATR	ataxia telangiectasia and RAD3-related
AUC	area under the plasma concentration-time curve
AUC ₀₋₂₄	area under the plasma concentration-time curve from 0 to 24 hours
BCRP	breast cancer resistance protein
BER	base excision repair
BID	twice daily
Bp	base-pair
BPI-SF	Brief Pain Inventory – Short Form
BRCA	breast cancer 1 or breast cancer 2
BRCA1/2	breast cancer gene 1 or breast cancer gene 2
BMT	bone marrow transplant
CBR	clinical benefit rate
CFR	Code of Federal Regulations
CI	confidence interval
CL	Clearance
CL/F	apparent total clearance of drug after oral administration
CLIA	Clinical Laboratory Improvement Amendments
C _{max}	maximum plasma concentration
CNS	central nervous system
CR	complete response
CRF	case report form
CRM	continual reassessment model
CRP	C-reactive protein
CRPC	castration-resistant prostate cancer
CT	computed tomography

CTCAE	Common Terminology Criteria for Adverse Events
ctDNA	circulating cell-free tumor DNA
CV	coefficient of variation
CYP	cytochrome P450
DILI	drug-induced liver injury
DLT	dose-limiting toxicities
DMC	data monitoring committee
DNA	deoxyribonucleic acid
DOR	duration of response
DSB	double-strand breaks
EC	European Commission
EC ₅₀	concentration producing 50% of maximum effect
ECG	Electrocardiogram
ECOG	Eastern Cooperative Oncology Group
eCRF	electronic Case Report Form
EDC	electronic data capture
EMA	European Medicines Agency
EOC	epithelial ovarian cancer
EQ-5D-5L	EuroQol 5 dimensions 5 level questionnaire
EU	European Union
F	Bioavailability
FACT-P	Functional Assessment of Cancer Therapy – Prostate
FD & C	colorants that have been approved by the Food and Drug Administration for use in food, drugs and cosmetics
FDA	Food and Drug Administration
FFPE	formalin-fixed paraffin-embedded
FMI	Foundation Medicine, Inc.
FSH	follicle stimulating hormone
FTC	fallopian tube cancer
gBRCA	germline breast cancer gene 1 or 2 mutation
GCP	Good Clinical Practice
GFR	glomerular filtration rate
GDPR	General Data Protection Regulation
GI	Gastrointestinal
GLP	Good Laboratory Practice
H & E	hematoxylin and eosin
HDP	hydroxydiphosphonate
HDPE	high-density polyethylene
HIPAA	Health Information Portability and Accountability Act
HIV	human immunodeficiency virus
HPMC	hydroxypropyl methylcellulose

HGSOC	high-grade serous ovarian cancer
HNSTD	highest non-severely toxic dose
HPLC	high-performance liquid chromatography
HR	hazard ratio
Hr	hour
HRD	homologous recombination deficiency
HRR	homologous recombination repair
IB	Investigator's Brochure
IC ₅₀	50% inhibitory concentration
ICF	Informed Consent Form
ICH	International Council for Harmonisation
ICMJE	International Committee of Medical Journal Editors
IEC	Independent Ethics Committee
IND	Investigational New Drug Application
INR	international normalized ratio
IRB	Institutional Review Board
IRR	independent radiological review
ITT	intent-to-treat
IUD	intrauterine device
IUS	intrauterine system
IWRS	Interactive Web Response System
IV	Intravenous
K _i	inhibition constant
K _{ic}	inhibition constant competitive
LHRH	luteinizing hormone-releasing hormone
LOH	loss of heterozygosity
MATE	multidrug and toxin extrusion transporter
mCRPC	metastatic castration-resistant prostate cancer
MDP	methylene diphosphonate
MDR1	multidrug resistance protein 1
MDS	myelodysplastic syndrome
MRI	magnetic resonance imaging
mRNA	messenger ribonucleic acid
MRP	multidrug resistance associated protein
MS	mass spectrometry
MTD	maximum tolerated dose
NAD	nicotinamide adenine dinucleotide
NADPH	nicotinamide adenine dinucleotide phosphate
NCI	National Cancer Institute
OAT	organic ion transporter
OCT	organic cation transporter

ORR	objective response rate
OS	overall survival
P _{app}	apparent permeability coefficient
PARP	poly(ADP-ribose) polymerase
PCWG3	Prostate Cancer Working Group 3
PD	progressive disease (in context of disease monitoring)
PDX	patient-derived xenograft
PEG	polyethylene glycol
PET	positron emission tomography
PFS	progression-free survival
P-gp	P-glycoprotein
PK	pharmacokinetic(s)
PLD	pegylated liposomal doxorubicin
PPC	primary peritoneal cancer
PR	partial response
PRO	Patient-reported Outcome
PSA	prostate-specific antigen
PV	pharmacovigilance
QD	once daily
RAD51C	RAD51 homolog C
RAD51D	RAD51 homolog D
RBC	red blood cell
RECIST	Response Evaluation Criteria in Solid Tumors
RP2D	recommended Phase 2 dose
rPFS	radiologic progression-free survival
SAE	serious adverse event
SAP	statistical analysis plan
sBRCA	somatic breast cancer gene 1 or 2 mutation
SD	stable disease (in context of disease monitoring)
SOC	system organ class
SOP	Standard Operating Procedure
SSB	single-strand break
t _{1/2}	terminal half-life
tBRCA	tumor tissue mutation in BRCA1 or BRCA2, includes gBRCA and sBRCA
TEAE	treatment-emergent adverse event
T _{max}	time of occurrence of C _{max}
TMZ	Temozolomide
UGT	uridine diphosphate-glucuronosyl transferase
UK	United Kingdom
ULN	upper limit of normal

Upper case gene/protein names	Gene and protein names should be in italics and plain text, respectively, based on HUGO Gene Nomenclature Committee guidelines. However, in this document mutations which occur at both the gene and protein level are often discussed. Therefore for enhanced readability, gene and protein names are written in plain text
US	United States
USAN	United States Adopted Name
USP	US Pharmacopeia
V_{ss}	volume of distribution at steady-state
WBC	white blood cell
wt	wild-type

